**Figure 1: White Blood Cell Count and Absolute Lymphocyte Count**

[figure not shown]
**Figure 2: Absolute Number of CD8+, CD4+ and NK Cells**

Extensive PK was not performed in the animals receiving CIV rhIL-15, with only single time points on days 2 and 10 of infusion assessed. IL-15 levels reached the low ng/mL level on day 2 and ranged from 2.1 to approximately 6.3 ng/mL. Day 10 values during course 1 were generally lower. During subsequent courses the peak values observed were also in the ng/mL range, and in some animals, the day 10 values were higher than on day 2 (Figure 3). Day 17 and 24 samples (7 and 14 days after last day of infusion) had no detectable human IL-15 in the serum. The greater than 20-fold expansion of IL-15-responsive cells (presumably IL-15 receptor-positive cells) might contribute to the decrease in free circulating rhIL-15 measured at the day 10 time point, but the differences in IL-15 PK during course 2 as well as decreased course 2 and 3 leukocytosis are not yet explained and remain under investigation. Preclinical testing of rh cytokines in NHP provides valuable preclinical information for clinical trials; species differences will occasionally cause confounding results, but these issues do not diminish the provocative positive results from

these experiments.

**Figure 3: IL-15 Levels**

An important cause of the PK and stimulation differences to be eliminated was the development of rhesus macaque (rm) antibodies against human IL-15. The rhesus monkeys were evaluated for the presence of rm anti-IL-15 antibodies, and in the monkeys receiving CIV IL-15, 3 of 6 animals developed detectable levels of antibodies at some point during the test period. One animal became positive after the first course with a boost in the IL-15 titer in this animal positive after the second course. Another CIV animal became low titer positive after the second course and remained positive in the pre-course 3 assessment, and a third animal was observed to have antibodies to IL-15 that were just above the lower limit of detection of the assay in the pre-course 3 assessment. All 3 animals continued to have elevated titers after completing the third course of CIV IL-15. While the test animal that demonstrated anti-IL-15 antibodies after the first course of treatment and had the highest anti-cytokine titers throughout the experiments had somewhat lower WBC and ALC values measured for the first treatment course, this particular macaque and none of the other antibody-positive animals showed substantial differences in their lymphocyte expansion or pattern of lymphocyte subpopulations compared to animals that tested negative for anti-IL-15 antibodies. The underlying causes of the difference in the immune response observed in courses 2 and 3 treatment has not been fully explained and is still being assessed with samples obtained during these experiments.

The macaques also had an inflammatory cytokine analysis performed. At the time points measured in this study, IL-8 was the only cytokine that gave values that were within the detection range of the standard curve, while all other samples had signals below the 2.4 pg/mL test standard. It is possible that evaluation of secondary cytokine induction would be more successful if the focus was on early time points such as 4, 8 and 24 hours after initiation of continuous infusion that have been measured in the ongoing IVB trial and are planned for this trial.

Compared to NHP that had received 20 mcg/kg/daily as an IVB for 12 days, the animals receiving 20 mcg/kg/daily CIV for 10 days had more constitutional and gastrointestinal side effects, as well as biochemical laboratory abnormalities that were most noticeable after the

first week of course 1 treatment coinciding with the period of greatest lymphocytosis. These side effects, biochemistry abnormalities and lymphocytosis, were somewhat blunted during the second and third treatment course for reasons that are again not yet entirely clear.

#### 1.2.1.4 Clinical Experience from the Completed IV Bolus Phase I Study

The first in-human (FIH) trial that tested a daily 30-minute infusion (IVB) for 12 days in subjects with metastatic melanoma and renal cell cancer has been completed after treating 18 subjects (58). Doses assessed in this trial were 3, 1 and 0.3  $\mu\text{g}/\text{kg}$ ; with the 0.3  $\mu\text{g}/\text{kg}$  dose determined to be the MTD for this schedule. DLTs at the 3  $\mu\text{g}/\text{kg}$  dose were grade 3 hypotension and grade 3 thrombocytopenia; DLTs at the 1  $\mu\text{g}/\text{kg}$  dose were grade 3 elevations of transaminases. One Serious Adverse Event (SAE) grade 3 pneumonitis possibly related to rhIL-15 treatment occurred during a subject's second cycle of treatment. The frequency and severity of common cytokine related toxicities such as fever, rigors, capillary leak syndrome and edema were generally proportional to the dose of rhIL-15. Abnormal laboratory results were seen in all subjects and most often were CTC grade 1 or 2 events. Laboratory adverse events (AEs) were less clearly proportional to the dose of rhIL-15 both in frequency and severity as indicated by low and transient occurrence of grade 2 laboratory AEs in the 3  $\mu\text{g}/\text{kg}$  cohort, whereas both DLTs in the 1  $\mu\text{g}/\text{kg}$  dosing cohort were elevated AST/ALT. The 0.3  $\mu\text{g}/\text{kg}$  dosing cohort also had a high frequency of laboratory abnormalities including non-DLT grade 3 elevation of ALT/AST in one patient. There was a consistent temporal pattern of post-treatment AEs most clearly seen in 3  $\mu\text{g}/\text{kg}$  cohort with fever beginning approximately 2 to 2½ hours after the rhIL-15 infusions, then rigors followed almost immediately by decreased blood pressure (BP).

A similar but less severe set of post treatment toxicities were seen in the 1  $\mu\text{g}/\text{kg}$  subjects with chills rather than rigors, less significant increases in temperature, but no appreciable BP changes. There was a very low frequency or absence of these post infusional events in the 0.3  $\mu\text{g}/\text{kg}$  dosing cohort. Serial analyses of inflammatory cytokine levels (IL-1 $\beta$ , IL-6, IL-8, IL-10 and TNF $\alpha$ ) showed marked increases in serum levels of these inflammatory cytokines that coincided with these clinical toxicities and was most closely matched with the IL-6 levels. As predicted by the NHP toxicology studies performed to support this trial appreciable expansion and activation was seen for T-cells and NK cells, but the increase in lymphocytes was statistically significant only for the group that received the 3  $\mu\text{g}/\text{kg}$  dose that produced a 10-fold increase in NK cells, a more than 3-fold increase in T-cells mostly due to expansion of the terminally differentiated (memory and effector memory) CD8 $^{+}$  cells. The half-life ( $t_{1/2}$ ) was approximately 2 1/2 hours with Cmax 47,800, 15,900 and 1260 pg/mL respectively for the 3 dose levels tested. There were no clinical responses, with stable disease as a best response. However, 5 subjects manifested a decrease between 10 and 30% in their marker lesions, with 2 of these subjects having improvement or clearance of some lung lesions.

#### 1.2.1.6 Rationale for Phase I Evaluation of Repeated Cycles of rhIL-15 given on either a 10-day or 5-day CIV Schedule

When rh cytokines first became widely available for clinical trials, in addition to identifying appropriate dosing, different routes of administration (IVB, CIV, SC, intracavitary or IP) and schedules were evaluated. At the time the NCI Surgery Branch was piloting the three times daily (tid) IVB regimen that has become the standard HD IL-2 regimen, the so called “West” regimen with CIV HD IL-2 given over 5 days (120 hours) was being investigated in numerous clinical trials. The initial publication for this CIV regimen reported a higher response rate (RR) along with a similar spectrum of typical cytokine-induced side effects, but did not show the roller coaster (peak valley) course of BP, capillary leak and widened A-a gradient characteristic of the tid HD IL-2 regimen (59, 60). An important feature that made this treatment plan popular with certain practitioners was the gradual emergence of more serious or DLTs as the patient’s limit of tolerance was approached more slowly. The every 8 hour IVB HD IL-2 regimen can be characterized by acute onset of respiratory and vascular toxicities with significant variation depending on the active drug levels related to the most recent dose; these toxicities can occur early in the treatment cycle. In addition, patients can rapidly transition from a tolerable treatment course to severe complications in the space of a few consecutive doses (36). With CIV HD IL-2, there is no rapid variation in immune activation or secondary cytokine levels, and the patients approach their unacceptable toxicity threshold at a steadier and usually slower rate. This CIV HD IL-2 regimen has not been popular for quite some time, but lower-dose CIV regimens have been evaluated by the French Immunotherapy Group (60), in the treatment of patients with HIV (61). It is also interesting to note that recently a positive phase III licensing trial for the anti-GD2 chimeric antibody ch14.18 in the treatment of advanced pediatric neuroblastoma (62) used a CIV IL-2 regimen as part of a multi-agent treatment. This trial was initiated with a 6-week cycle length based on data from the NHP toxicology study that validated the treatment regimen given every 6 weeks. An ongoing clinical multicenter trial (NCI protocol 13-C-0045 or CITN 11-02) evaluating a similar rhIL-15 SC outpatient regimen (M-F for 2 consecutive weeks) has demonstrated that rhIL-15 can safely be given on a 4-week schedule. Patients need to demonstrate some evidence of a clinical response during their first 2 cycles of treatment to be eligible for additional treatment cycles. The clinical course

## **2 ELIGIBILITY ASSESSMENT AND ENROLLMENT**

### **2.1 ELIGIBILITY CRITERIA**

#### **2.1.1 Inclusion Criteria**

- 2.1.1.1 Age  $\geq$  18 years.
- 2.1.1.2 Patients must have histologically confirmed (by the NCI Pathology Department) solid tumor malignancy or lymphoma that is metastatic or unresectable and for which standard curative or palliative measures do not exist or are associated with minimal patient survival benefit (as defined by the Lymphoid Malignancies Branch physicians) or if the patient refuses standard of care treatment. Enrollment of patients with tumors that can be safely biopsied is encouraged.
- 2.1.1.3 Patients must have evaluable or measurable disease, defined as at least one lesion that can be accurately measured in at least one dimension (longest diameter to be recorded for non-nodal lesions and short axis for nodal lesions) as  $\geq$ 20 mm with conventional techniques or as  $\geq$ 10 mm with spiral CT scan. See Section **6.2** for the evaluation of measurable disease.
- 2.1.1.4 Patients must have recovered to  $\leq$  grade 1 CTCAE v4 from toxicity of prior chemotherapy or biologic therapy and must not have had prior chemotherapy or biologic therapy within 4 weeks (6 weeks for nitrosoureas or mitomycin C, 8 weeks for UCN-01).
- 2.1.1.5 Patients on bisphosphonates for any cancer or on hormone therapy for prostate cancer will not need to discontinue this therapy to be eligible. However, patients with prostate cancer will need to have metastatic prostate cancer that has progressed despite hormonal therapy. Castrate testosterone levels occur within hours after castration and within 2 to 3 weeks of a luteinizing hormone-releasing hormone agonist. The current standard is to continue androgen suppression despite progressive disease.
- 2.1.1.6 DLCO/VA and FEV-1.0  $\geq$  60% of predicted on pulmonary function tests.
- 2.1.1.7 Serum creatinine of  $\leq$  1.5 X the upper limit of normal.
- 2.1.1.8 AST and ALT  $<$  2.5 x the upper limit of normal.
- 2.1.1.9 Absolute neutrophil count  $\geq$  1,500/mm^3 and platelets  $\geq$  100,000/mm^3.
- 2.1.1.10 Karnofsky performance status  $\geq$  70% or ECOG  $\leq$  1 (see **APPENDIX A**)
- 2.1.1.11 Subjects with inactive central nervous system (CNS) metastasis are eligible. Inactive CNS metastasis is defined as: no signs of cerebral edema after successful definitive treatment of brain metastases (surgical resection, whole brain irradiation, stereotactic radiation therapy, or a combination of these) with stable or improved radiographic appearance on MRI scan at least 1 month after completion of treatment.

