### Eligibility Criteria:

- Patients  $\geq 18$  years-old, ECOG PS  $\leq 1$ , with pathologically confirmed metastatic unresectable cancers for which curative or palliative measures either do not exist or are not associated with a survival advantage.
- Patients with measurable or evaluable disease, normal organ and bone marrow function

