#### **2.1.2 Exclusion Criteria**

- 2.1.2.1 Patients who have received any systemic corticosteroid therapy within 3 weeks prior to the start of therapy with the exception of physiological replacement doses

of cortisone acetate or equivalent.

- 2.1.2.2 Patients who have received any cytotoxic therapy, immunotherapy, antitumor vaccines, monoclonal antibodies or major surgery in the 4 weeks prior to the start of the study.
- 2.1.2.3 Life expectancy of less than 3 months.
- 2.1.2.4 Patients with more than 30% replacement of hepatic parenchyma by tumor or any history of drug related hepatic encephalopathy.
- 2.1.2.5 History of complex ventricular or supraventricular arrhythmias.
- 2.1.2.6 Documented HIV, active bacterial infections, active or chronic hepatitis B, or hepatitis C.
  - A positive hepatitis B serology indicative of previous immunization (i.e., HBsAb positive and HBc Ab negative), or a fully resolved acute hepatitis B infection is not an exclusion criterion.
  - A positive hepatitis C serology is an exclusion criterion.
- 2.1.2.7 Concurrent anticancer therapy (including other investigational agents), with the exception of hormone therapy for prostate cancer (see Section [2.1.1.5](#)).
- 2.1.2.8 Active CNS metastasis (inactive CNS metastasis is defined in Section [2.1.1.11](#)).
- 2.1.2.9 History of severe asthma or presently on chronic inhaled corticosteroid medications (patients with a history of mild asthma controlled with inhaled bronchodilators are eligible).
- 2.1.2.10 History of autoimmune disease, with the exception of an autoimmune event associated with prior ipilimumab (anti-CTLA-4) therapy that has been completely resolved for more than 4 weeks.
- 2.1.2.11 Inability or refusal to practice effective contraception during therapy or the presence of pregnancy or active breastfeeding (men and women of childbearing potential must use an effective method of birth control or abstinence during treatment and for 4 months after completion of treatment).
- 2.1.2.12 Cognitive impairment, history of medical or psychiatric disease, other uncontrolled intercurrent illness, active substance abuse, or social circumstances, which in the view of the Principal Investigator (PI), would preclude safe treatment or the ability to give informed consent.

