## **2.2 SCREENING EVALUATION**

Screening evaluation must be performed to determine eligibility within 28 days prior to patient receiving any study intervention, except as indicated below.

- 2.2.1 Complete medical history and physical examination with vital signs and documentation of all measurable or evaluable abnormalities.
- 2.2.2 Computerized tomography (CT) scan of the chest, abdomen, and pelvis. (CT and/or MRI films from outside institution performed within 28 days prior to enrollment may be used to determine eligibility. Same films may be used as baseline if done within 28 days prior to starting treatment.)

- 2.2.3 MRI or contrast-enhanced CT scan of the brain for melanoma subjects or subjects with complaints and/or physical findings suspicious for occult CNS metastasis.
- 2.2.4 Documentation of Karnofsky Performance Score  $\geq 70\%$  or ECOG  $\leq 1$  (see **APPENDIX A**).
- 2.2.5 Verification that the NCI Laboratory of Pathology has confirmed the histology prior to patient registration (No Time Frame). Pathological confirmation of diagnosis can be carried out on available slides from either the primary diagnostic biopsy or subsequent biopsies performed either at the Clinical Center or outside institutions. If necessary, the specimen blocks will be obtained for special stains and other evaluation as deemed necessary to confirm the diagnosis of cancer. If the original pathological material or other diagnostic biopsies are not available, or if there is uncertainty concerning the diagnosis, a repeat biopsy may be undertaken to confirm the diagnosis of cancer.
- 2.2.6 Complete blood count (CBC) with differential and platelet count Acute Care Panel (sodium, potassium, chloride, CO2, glucose, BUN, creatinine); Hepatic panel (alkaline phosphatase, ALT, AST, total and direct bilirubin), LDH, Mineral panel (serum calcium, phosphate, magnesium and albumin) and ammonia level.
- 2.2.7 Serum pregnancy test in women of childbearing potential.
- 2.2.8 Thyroid function tests to include a serum thyroxine (T4) and thyroid-stimulating hormone (TSH).
- 2.2.9 Anti-nuclear antibodies (ANA), rheumatoid factor (RF) and anti-thyroid antibodies
- 2.2.10 Urinalysis.
- 2.2.11 12 lead EKG.
- 2.2.12 Hepatitis B Surface Antigen, Hepatitis B Surface Antibody, Hepatitis B core Antibody and Hepatitis C: HIV 1/2 serology.
- 2.2.13 Pulmonary function tests with DLCO.

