### **2.4 BASELINE EVALUATION**

The following tests and procedures will be done within 28 days of initiating treatment with rhIL-15 (except as marked below). If baseline tests were already performed and meet the required time frames, they will not need to be repeated.

- 2.4.1 Baseline history with documentation of sites of disease, physical examination, vital signs and performance score.

- 2.4.2 Serum pregnancy test in women of childbearing potential must be repeated within 3 days prior to starting study drug.
- 2.4.3 CBC with differential, Acute Care Panel, Hepatic Panel, LDH and Mineral Panel must be repeated if not done within 2 weeks of starting study drug.
- 2.4.4 Reticulocyte Count
- 2.4.5 Serum immunoglobulin levels
- 2.4.6 Troponin T or I, based on availability of test in Department of Lab Medicine (DLM)
- 2.4.7 HLA typing (A, B, C, DR, DQ)
- 2.4.8 Serum tumor marker (PSA, CEA, and CA125) assessment if applicable (within 7 days prior to initiating treatment with rhIL-15)
- 2.4.9 CT scan of the chest, abdomen and pelvis, or MRI if CT scan is not sufficient or contraindicated
- 2.4.10 Other imaging studies may be done to document disease as appropriate and at the direction of the PI.
- 2.4.11 Baseline flow cytometry to assess lymphocyte sets and subsets (see Section [5.1.2](#)):
  - 2.4.11.1 One 10-mL lavender-top tubes to Clinical Center Dept. of Lab. Medicine for Lymphocyte Phenotype IL-15 FACS panel.
  - 2.4.11.2 Two lavender-top tubes to the Clinical Support Laboratory in Frederick for special FACS analysis.
- 2.4.12 One 4-mL Serum Separator Tube (SST) tube to the Clinical Support Laboratory in Frederick for inflammatory marker and cytokine analysis (see Section [5.1.3](#)).
- 2.4.13 Optional Tumor Biopsy (see Section [5.1.5](#))

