activated T-cells and cytokine therapy will have a significant leukocytosis ([67](#)). Even though these cells are activated and generally large lymphocytes, toxicities seen in leukemic patients with elevated WBC counts are not encountered and therapy is not interrupted based purely on an arbitrary WBC number. In the completed IVB trial and in this protocol, we have observed most commonly during the first 7 days of treatment transient increases in liver function tests (alkaline phosphatase, alanine aminotransferase [ALT] and aspartate aminotransferase [AST] which usually begin to improve while the subject continues treatment and have not been associated with any clinical signs of hepatotoxicity. During the IVB trial, treatment was discontinued for grade 3 elevations ( $> 5$  times ULN) of AST and/ALT in 2 subjects treated at the 1 mcg/kg dose level who otherwise were tolerating their treatment very well. Some subjects previously treated in this protocol have had less significant elevations that have also resolved without incident, DLTs or clinical sequelae. HDIL-2 subjects commonly have abnormalities of their LFTs in many occasions much more abnormal than we have observed in the rhIL-15 subjects and continue their treatment ([59](#), [60](#)). Similar transient increases which resolve spontaneously most often with continued rhIL-15 or in all cases after treatment is stopped have also not been associated clinical hepatotoxicity with the one exception discussed in Section [1.2.1.6](#). We believe that the clinical experience with rhIL-15 in all three trials with the additional limitation on degree of hepatic tumor replacement allows continuation of the DLT exception with regards to ALT, AST, alkaline phosphatase, total and direct bilirubin.

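### Section 2.1 sets no entry limit for bilirubin, although it limits creatinine and AST/ALT and already measures bilirubin at screening (optional, low-cost safety improvement)

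*Combined protocol and SAP*

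**What the plan says.** Items 2.1.1.6 to 2.1.1.9 set numeric limits for lung function, creatinine (at most 1.5 × ULN), AST and ALT (below "2.5 x the upper limit of normal"), neutrophils and platelets. No item in 2.1.1 or 2.1.2 sets a limit for bilirubin.

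Bilirubin appears elsewhere in the protocol:

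- Screening, item 2.2.6, includes it: "Hepatic panel (alkaline phosphatase, ALT, AST, total and direct bilirubin".
- Baseline, item 2.4.3, says of the same panel: "Hepatic Panel, LDH and Mineral Panel must be repeated if not done within 2 weeks of starting study drug".
- The adverse event list in Section 11.1.2 names a bilirubin increase among events with a possible relationship to rhIL-15.
- Section 3.2.1 exempts grade 3 total or direct bilirubin from DLT if it lasts under 7 days and there are no clinical signs of hepatic dysfunction.

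Provisions that bear indirectly on liver function at entry are:

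- the précis, which asks for "normal organ and bone marrow function";
- item 2.1.1.4, recovery to at most "grade 1 CTCAE v4 from toxicity of prior chemotherapy or biologic therapy";
- item 2.1.2.4, which excludes "Patients with more than 30% replacement of hepatic parenchyma by tumor";
- item 2.1.2.6, which excludes active or chronic hepatitis B and positive hepatitis C serology;
- item 2.1.2.12, which leaves it to the principal investigator to exclude medical disease or "other uncontrolled intercurrent illness" that would preclude safe treatment.

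**The concern.** The protocol collects bilirubin before treatment but gives no threshold for acting on it. A patient with raised bilirubin that is not due to prior therapy, with transaminases in range and no more than 30% hepatic replacement, meets every numeric criterion. That patient could start a 5-day infusion of a drug for which bilirubin increase is a listed possible effect, with little room before grade 3.

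The stake is mainly patient safety at entry. There is a smaller link to the primary endpoint. A grade 3 bilirubin that is at least possibly related to the drug counts as a DLT once it has lasted 7 days, or sooner if clinical hepatic signs appear. A patient who starts high reaches grade 3 with a smaller rise, and Section 3.2.1 states no adjustment for baseline.

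Section 3.2 supports keeping the liver-test exception, bilirubin included, partly by pointing to the limit on hepatic tumor replacement. That limit concerns how much of the liver is tumor; it does not bound bilirubin.

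**Working it through.** **Is the limit really absent?** The inclusion items run from 2.1.1.1 to 2.1.1.11 and the exclusion items from 2.1.2.1 to 2.1.2.12 without a gap in numbering. None mentions bilirubin, so the absence is not an artifact of missing text.

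**Does another provision bound it?**

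| Provision | Why it does not bound bilirubin at entry |
|---|---|
| Précis, organ function | Carries no number |
| 2.1.1.4 | Covers only toxicity of prior chemotherapy or biologic therapy |
| 2.1.2.4 | Limits tumor replacement, not bilirubin |
| 2.1.2.6 | Covers viral hepatitis only |
| 2.1.2.12 | Depends on the investigator's judgement |
| 3.2.1, clinical signs end the exception | Acts only after treatment starts |
| 3.8.2, hepatic panels on days 1 to 6, 8 and 21; 3.5, early stopping for safety | Act only after treatment starts |

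**How much room would a cap leave?** Section 3.2 puts the grade 3 threshold for AST/ALT at more than 5 × ULN, where it reports that in the bolus trial "treatment was discontinued for grade 3 elevations". The AST/ALT entry limit therefore leaves a rise of 5 / 2.5 = 2.0-fold.

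The documents do not give the grade 3 threshold for bilirubin. I assume G = 3 × ULN and show 2.5 to 4. Rise needed to reach grade 3 = G / baseline:

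| Baseline bilirubin (× ULN) | G = 2.5 | G = 3 | G = 4 |
|---|---|---|---|
| 1.5 (proposed cap) | 1.67 | 2.00 | 2.67 |
| 2.0 | 1.25 | 1.50 | 2.00 |
| 2.5 | 1.00 | 1.20 | 1.60 |

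The baseline that gives the same 2.0-fold room as AST/ALT is G / 2 = 1.25, 1.5 or 2.0 × ULN.

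**How many patients would it cover?** The 10-day MTD has already been identified, so the line would apply to later patients on the three 5-day levels (7, 8 and 9).

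- All three levels evaluated, no expansion: 3 × 3 = 9 to 3 × 6 = 18 evaluable patients.
- Level 9 filled to nine: 3 + 3 + 9 = 15 to 6 + 6 + 9 = 21. This agrees with Section 8: 24 + 2 = 26 patients on levels 1 to 6, and 41 − 26 = 15, 47 − 26 = 21.
- The Schema makes the 5-day expansion conditional on at least one confirmed response, so 15 to 21 is not assured.
- If escalation stops early, the number is smaller.

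**The case against.** The strongest reply is that the sponsor considered hepatic risk and left the decision to clinical judgement. The investigator sees the bilirubin result before treatment and can exclude under 2.1.2.12. Hepatitis B and C are excluded, and Section 3.2 names bilirubin when it explains why the exception is acceptable. That section also refers to a hepatotoxicity case discussed in Section 1.2.1.6, part of which was not in the text I reviewed. All of this stands as mitigation, and it may keep most such patients out. It does not amount to a limit that can be enforced.

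Second, the choice of bilirubin can be called selective. Alkaline phosphatase is screened, sits in the same exception and has no entry limit either. The transient rises that Section 3.2 reports as observed are alkaline phosphatase, ALT and AST, not bilirubin. This also stands, and it is a reason to treat the point as optional.

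Third, the 2-fold comparison with AST/ALT is my benchmark, not the protocol's, and it rests on an assumed threshold. At G = 4 a patient entering at 2.0 × ULN has no shortfall; at G = 2.5 the proposed cap itself falls short, at 1.67-fold. The comparison illustrates the size of the gap and does not derive the cap.

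A reader might infer that the missing limit biases the MTD or changes the chance of escalating. The documents do not support that. A DLT needs at least possible relatedness as judged by the investigator, who can weigh a raised baseline, and no rate of raised bilirubin at entry is given. A reader might also infer a fault in the 7-day exception or the stopping provisions; none is shown.

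**Conclusion.** The omission is real, and filling it is a cheap, optional safety improvement. Section 2.1 bounds creatinine and AST/ALT but not bilirubin, and the existing protections narrow the gap without closing it. Under an assumed grade 3 threshold of 3 × ULN, a patient entering at 2.0 × ULN needs a 1.5-fold rise to reach grade 3 (1.25 to 2.0 over the range). At the proposed cap the figure is 2-fold (1.67 to 2.67). The number of patients who would enter with raised bilirubin is unknown, and the relationship of bilirubin increase to rhIL-15 is listed only as possible.

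**What to change.** Add one line to Section 2.1.1: total bilirubin ≤ 1.5 × ULN (in Gilbert syndrome, direct bilirubin within normal limits). Leave the DLT definition, the 7-day exception and alkaline phosphatase as they are.

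The 1.5 multiple is a conventional choice. It matches the creatinine multiple in 2.1.1.7 but is not derived from the documents. The Gilbert allowance is deliberate and has a price: such a patient with total bilirubin of 2.5 × ULN may still enter with only 1.2-fold room at the assumed threshold, and Section 3.2.1 grades total as well as direct bilirubin.

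The cost is one line in an amendment. No new test is needed, and the sample size and the DLT definition used for the 10-day MTD do not change. The downside is that a small, unquantified number of patients is screened out.
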